11.0 RISKS AND BENEFITS OF THE STUDY

This study may or may not provide any benefits to the subject. However, the data collected throughout the study may help to assess the effectiveness and safety of a new ablation technique: robotic-assisted transbronchial microwave ablation of oligometastatic tumors in the lung.

Procedural Risks

The procedural risks associated with the FLEX MC transbronchial ablation procedure are expected to be similar to those associated with diagnostic bronchoscopy as well as those associated with thermal ablation, which in extremely rare instances could lead to death. The Sponsor plans on mitigating these risks during the clinical study by careful patient selection, implementing intraprocedural stopping rules, and the establishment of an independent DSMB to monitor the study.

Most commonly known risks for diagnostic bronchoscopy and thermal ablation procedures in the lung are summarized below by expected frequency: extremely rare (< 0.01%), rare (0.01% - 0.1%), uncommon (0.1% - 1%), common (1% - 10%), and very common (> 10%):

Known Risks for: Diagnostic Bronchoscopy	Known Risks for: Transbronchial Thermal Ablation Procedures in the Lung

RARE:
 
 Cardiovascular events 
UNCOMMON:
 
 Breathing difficulty Vocal cord spasm Vomiting Dizziness Bronchial spasm (muscle contraction of the airway) Hypoxemia (shortness of breath due to low levels of oxygen in the blood) 
COMMON:
 
 Pneumothorax (when air leaks into the space between the lungs and the chest wall) Hemorrhage (bleeding requiring medical intervention) 	
RARE:
 
 Bronchopleural fistula (abnormal passageway that develops between the large airways in the lungs and the space that lines the lungs) 
UNCOMMON:
 
 Air/Gas embolism (blockage or obstruction of a blood vessel) Infection 
COMMON:
 
 Pneumothorax (when air leaks into the space between the lungs and the chest wall) Hemorrhage (bleeding requiring medical intervention) Pleural effusion (buildup of fluid in tissues lining the lungs and the chest requiring tube drainage) Pneumonia 
VERY COMMON

	
 • Pain • Post-ablation syndrome
--	--

Anesthesia Risks

Subjects will be put under general anesthesia for the study procedure. Common risks of anesthesia include nausea, vomiting, dizziness, drowsiness, and shivering. These are typically mild, short-lived symptoms that are easily managed. In rare instances, liver toxicity and cardiovascular events may occur.

Intubation Risks

There are some risks related to the intubation procedure as well as passing the bronchoscope into the airway. These rare risks include intubation-related airway injury, injury to teeth or dental work, bleeding, lung injury, and aspiration.

Radiation Risks

The required CT (computerized tomography) images will expose subjects to radiation. The total radiation exposure for each subject will be dependent on the number of CTs per subject and the type of CTs, as well as many other factors, such as the manufacturer of the scanning equipment. Conventional CT has an average radiation range 1mSv to 10mSv, while the average radiation range for cone beam CT is 1mSv to 5mSv. Recent pilot studies of bronchoscopic microwave ablation have reported a mean radiation dose of 27.8 mSv.²² This is comparable to dose exposure seen in other common image guided procedures, such as percutaneous coronary intervention (15 mSv), atrial fibrillation ablation (17 mSv), and transcatheter aortic valve implantation (37 mSv).²⁹ The total radiation exposure to the subject during the ablation procedure will be captured.

Device Risks

The device risks associated with the FLEX MC procedure includes those of a diagnostic bronchoscopy as well as those associated with thermal ablation. These primarily include pneumothorax, unintended thermal damage, embolism, excessive bleeding, premature end of procedure, and in rare instances could lead to death. These risks have been identified and mitigated through the risk management tools compliant with ISO 14971 during the development of the MONARCH and the FLEX Systems. A summary of the more common device risks and design mitigations are listed below.

Device Risk	Design Mitigation(s)
Pneumothorax	MONARCH platform incorporates pre-procedure planning, facilitates multiple imaging modalities during navigation and direct visualization via camera in the MONARCH bronchoscope. The NEUWAVE FLEX probe tip is highly visible under imaging to allow proximity to the pleura to be assessed throughout the procedure.
Unintended thermal damage due to ablation zone shape	NEUWAVE FLEX System includes a Time-Power onscreen ex-vivo ablation zone reference for the user. NEUWAVE FLEX System uses CO ₂ gas to cool the FLEX probe while continuously monitoring temperature at three locations on the probe.

Unintended thermal damage due to probe placement	MONARCH platform incorporates pre-procedure planning, multiple imaging modalities during navigation and direct visualization via camera in the MONARCH bronchoscope. The NEUWAVE FLEX probe is highly visible under imaging to allow probe location to be assessed throughout the procedure.
Embolism due to CO ₂ cooling gas leak	NEUWAVE FLEX Probe is designed and tested to safely contain high pressure CO ₂ gas in a sealed system. In addition, the user is required to perform a functional probe test that includes a CO ₂ leak check. The system will not allow energy delivery if a leak is detected.
Excessive bleeding due to organ laceration	MONARCH facilitates multiple imaging modalities during navigation and includes direct visualization via camera in the MONARCH bronchoscope. NEUWAVE FLEX Probe tips are coated with non-stick material designed to reduce insertion/removal force and help prevent ablated tissue adhesion to the probe tip.

Benefits

In patients with a controlled primary malignancy who develop oligometastatic disease in the lung for which their treatment team believes local tumor control is necessary, FLEX MC provides a treatment option via complete tumor ablation. This option may minimize some of the risks associated with other options to achieve local control including surgery, SBRT, or percutaneous approaches. In addition, FLEX MC may offer patients less of a decrement in health-related quality of life as compared to other currently available therapies. The risks of FLEX MC are those associated with known risks of bronchoscopy and thermal ablation, which are well established procedures. With the existing robust risk mitigations in place (described above), the Sponsor's assessment is that the risks are adequately analyzed, evaluated, controlled, verified for effectiveness, and the benefits outweigh the risks in this patient population.

12.0 ASSESSMENT OF SAFETY

Subjects will be evaluated for AEs and SAEs from the time of consent based on the following descriptions:

- Perioperative AEs will be captured from the time of subject consent through 30-days post any ablation procedure (i.e., the original ablation as well as any re-ablation) regardless of relationship to the study device or procedure.
- AEs that are deemed related to the study device or procedure will be captured 30-days post any ablation procedure (i.e., the original ablation as well as any re-ablation) through the end of the study or early discontinuation.
- Serious adverse events (SAEs) will be captured from the time of subject consent through the end of the study or early discontinuation regardless of relationship to the study device or procedure.

Investigators should remind study subjects to notify and/or see them or their study team first, when possible, if they experience any adverse events versus seeking treatment elsewhere.

Ongoing Review

The Sponsor will also review complications periodically, as per the study's Safety Management Plan.

12.1 Adverse Events

Adverse Event (AE)

For this study, an adverse event is defined as any untoward medical occurrence, unintended disease or injury, or any untoward clinical signs, including an abnormal laboratory finding, in a subject whether or not related to the study device or procedure.

Expected Morbidity/Anticipated Adverse Events

An expected morbidity/procedural complication is defined as an AE that is known to be common or usual in nature, severity, or incidence during ablation of the lung.

Serious Adverse Event (SAE)

It is the Investigator's responsibility to determine the "seriousness" of an AE using the protocol defined terms below. An SAE is an AE that results in one or more of the following for this study:

- Death;
- Serious deterioration in the health of the subject that resulted in any of the following:
 - Life threatening illness or injury;
 - Permanent impairment of a body structure or a body function;
 - Hospitalization or prolongation of patient hospitalization;
 - Medical or surgical intervention to prevent life-threatening illness or injury or permanent impairment to a body structure or a body function; or
 - Chronic disease.

- Fetal distress, fetal death, or a congenital physical or mental impairment or birth defect.

Notes:

1. Progression of the disease under study should not be reported as an SAE.
2. "Death" should not be reported as an AE. The cause of death should be reported as an AE. The only exception is "Sudden Death" when the cause is unknown.
3. Planned hospitalization for a pre-existing condition should not be considered an SAE.
4. A procedure required by the protocol should not be considered an SAE, unless the subject experiences a serious deterioration in health or hospitalization is prolonged.

The Sponsor will review all applicably reported AEs and SAEs according to the current Safety Monitoring Plan.

Unanticipated Adverse Device Event (UADE)

Any SAE caused by, or associated with, the device, if that event was not previously identified in nature, severity, or degree of incidence in the protocol or Investigator Brochure, or any other unanticipated serious problem associated with the device that relates to the rights, safety, or welfare of subjects.

Investigators are required to submit a report of a UADE to the Sponsor and the reviewing IRB as soon as possible, but no later than **72 hours** after the investigator first becomes aware of the event.

Sponsors must immediately conduct an evaluation of a UADE and report the results of the evaluation to FDA, all reviewing IRBs/ECs, and participating investigators within **10 working days** after the Sponsor first receives notice of the event.

SEVERITY OF ADVERSE EVENTS

It is the Investigator's responsibility to assess the severity of an AE. AE severity in this study will be determined using the current version of the Common Terminology Criteria for Adverse Events (CTCAE). The CTCAE uses Grades 1 through 5 with unique clinical descriptions of severity for each AE based on the general guidelines, provided below. Please note that a change in severity, or grade, may constitute a new reportable AE.

- Grade 1: Mild; asymptomatic or mild symptoms; clinical or diagnostic observations only; intervention not indicated;
- Grade 2: Moderate; minimal, local, or noninvasive intervention indicated; limiting age-appropriate instrumental activities of daily living (ADL);
- Grade 3: Severe or medically significant but not immediately life-threatening; hospitalization or prolongation of hospitalization indicated; disabling; limiting self-care ADL (e.g., bathing, dressing, and undressing, feeding self, using the toilet, taking medications, and not bedridden);
- Grade 4: Life-threatening consequences; urgent intervention indicated; and
- Grade 5: Death related to AE.

Note: A semi-colon indicates "or" within the description of the grade.

RELATIONSHIP OF ADVERSE EVENTS

It is the Investigator's responsibility to assess the relationship between all AEs and SAEs and the study procedure and device. The following guidelines should be used in determining the relationship of an AE to a device, study procedure, or other causality:

Not Related	
Relationship to the device or procedure can be excluded when:
 
 • The event has no temporal relationship with the use of the device or the procedures related to the device; • The event does not follow a known response pattern to the device or procedure (if the response pattern is previously known) and is biologically implausible; • The discontinuation of the device application or the reduction of the level activation/exposure (when clinically feasible) and reintroduction of its use (or increase of the level of activation/exposure), does not impact the event; • The event involves a body-site or an organ that cannot be affected by the device or procedure; • The event can be attributed to another cause (e.g., an underlying or concurrent illness/clinical condition, an effect of another device, drug, treatment, or other risk factors); and • The event does not depend on a false result given by the device used for diagnosis, when applicable. 
Note: To establish the non-relatedness, not all the criteria listed above might be met at the same time, depending on the type of device/procedure and the event.

Possible*	
The relationship with the use of the device or procedure is weak but cannot be ruled out completely. Alternative causes are also possible (e.g., an underlying or concurrent illness/condition and/or an effect of another device, drug, or treatment). Cases where relatedness cannot be assessed, or no information has been obtained should also be classified as possible.

Probable*	
The relationship with the use of the device or procedure seems relevant and/or the event cannot reasonably be explained by another cause.

Causal Relationship*	
The event is associated with the device or with procedure beyond reasonable doubt when:

- The event is a known side effect of the product category the device belongs to or of similar device and procedures;
- The event has a temporal relationship with the device uses/application or procedures;
- The event involves a body-site or organ that:
 - The device or procedures are applied to; or
 - The device or procedures have an effect on.
- The event follows a known response pattern to the device (if the response pattern is previously known);
- The discontinuation of the device application (or reduction of the level of activation/exposure) and reintroduction of its use (or increase of the level of activation/exposure), impact on the event (when clinically feasible);
- Other possible causes (e.g., an underlying or concurrent illness/clinical condition and/or an effect of another device, drug, or treatment) have been adequately ruled out;
- Harm to the subject is due to error in use; and
- The event depends on a false result given by the device used for diagnosis, when applicable.

To establish the relatedness, not all the criteria listed above might be met at the same time, depending on the type of device/procedure and the event.

*Indicates definitions of relationship that qualify to be recorded as part of the study for AEs only that occur more than 30-days any ablation procedure. All SAEs, regardless of relationship, will be collected.

12.2 Reporting Adverse Events

The Investigator is required to report all applicable non-serious AEs to the Sponsor within **14 days** of becoming aware of the event.

All SAEs and UADEs, regardless of relationship to the study device or procedure, are to be reported as soon as possible, but no later than **72 hours** after becoming aware of the event.

The study site will report applicable AEs and all SAEs to the Sponsor by entering the event into the EDC system via the AE eCRF, which will trigger an automated email to the Sponsor. Additional information, including the Investigator's assessment, may be added to the eCRF later. Any necessary medical management of the event will be recorded in the subject's medical record/source document. If the Sponsor requires supporting documentation or other information, the Sponsor will contact the study site.

Data related to AEs and SAEs will be collected until event resolution, until the event is considered stable, or until all attempts to determine the resolution of the event are exhausted.

All AEs and SAEs that are unresolved at study completion (or early termination) will be recorded as ongoing at study end.

The report of an AE or SAE by a site does not constitute an admission that study personnel or the user facility (hospital/clinic) caused or contributed to the event. The study site is responsible for submitting AEs/SAE to the reviewing IRB/EC, per their IRB/EC procedures.

In addition, the following information should be recorded:

- Onset date.
- Resolution date or date of death.
- Severity of the event.
- Action taken.
- Event status (ongoing at study end or resolved).
- Relationship of AE to the study devices.
- Relationship of AE to the study procedures.
- Indication of seriousness.
- Was AE anticipated.
- Time of AE (navigation, pre-ablation probe placement, ablation, post-ablation).

A report of a subject death or severe hemorrhage requiring intervention beyond local therapy (i.e., Nashville \geq grade 2 or CTCAE \geq grade 2) within 30 days of tumor ablation procedure will put enrollment on hold and require an investigation to determine if the death or hemorrhage was related to the ablation procedure. The investigation will be led by the independent Data Safety Monitoring Board, DSMB, described in Section 12.3.

Based on ongoing reviews of the data, additional stopping rules may be introduced as deemed appropriate.

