	
radiation therapy on the ablated lung side before completing the primary endpoint assessment (30 days post-ablation).
 
19. Subject who received systemic therapy (e.g., chemotherapy, targeted drug therapy, or immunotherapy) within 14 days prior to the planned study ablation procedure or those who plan to receive systemic therapy before completing the primary endpoint assessment (30 days post-ablation).
 
20. Uncontrolled hypertension pre-procedure (Visit 2). Defined as systolic blood pressure \geq 160mmHg and/or diastolic blood pressure \geq 100mmHg despite pharmacotherapy.
 
21. Subjects who have participated in an investigational drug or device research study within 30 days of enrollment that would interfere with the primary endpoint of this study.
 
22. Physical or psychological condition that would impair study participation.
 
23. Severe neuromuscular disease.
 
24. Subjects judged unsuitable for study participation by the Investigator for any other reason.
 
Intra-operative exclusion criteria that lead to stopping a procedure:
 
25. Inability to tolerate anesthesia.
 
26. Time of navigation to initiation of ablation longer than 60 minutes, per target tumor.
 
27. Bleeding estimated to exceed 50cc (visualization via the drainage system) or a Nashville grade 2 or higher intervention is required (see Appendix 2).
 
28. If the CBCT imaging after a bleeding episode obscures the radiographic visibility of the tumor such that the ablation probe/tumor relationship is not discernable, the procedure should be terminated.
 
29. Any presenting condition discovered intra-procedurally that in the opinion of the Investigator would make participating in this study not in the subject's best interest.

DSMB (Data Safety Monitoring Board)	
An independent Data Safety Monitoring Board (DSMB) will be commissioned to periodically review safety events from the study to ensure safety trends are consistent with the current safety profiles of the devices.
 
Specifically, a report of death or severe hemorrhage requiring intervention beyond local therapy (i.e., Nashville \geq grade 2 or CTCAE \geq grade 2) within 30 days of an ablation procedure will temporarily stop enrollment and require review by the DSMB.

Statistical Analyses	
The number and percentage of tumors achieving Technique Efficacy will be summarized and a confidence interval will be estimated.

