6.0 STUDY PROCEDURES

6.1 Procedure Description(s)

Adult subjects with at least one oligometastatic tumor ($\leq 2\text{cm}$) in the lung located in the outer two-thirds and not closer than 1cm to the pleura (including fissures) with colorectal, renal, or sarcoma histology will have transbronchial microwave ablation performed using the MONARCH Platform.

Multidisciplinary Team

With regard to the clinical treatment approach for each patient, this is best assessed and determined by a local (i.e., site) multidisciplinary team (MDT) (aka tumor board) directly caring for the subject. An MDT discussion will be required prior to subject ablation to determine or ensure 1) that all oligometastatic tumors present at Screening are deemed treatable, 2) the manner/timing that all disease sites will be treated, and 3) the appropriateness of subject inclusion in the study. The MDT will include, at a minimum, a medical oncologist, thoracic surgeon or appropriate surgical specialist, and radiation oncologist.

Screening and Planning

A CT scan of the lung is used at Screening to determine tumor details (e.g., size, location, and type, if available). Tumor size must be measured in 3 axes (axial, sagittal, and coronal).

A maximum of two ipsilateral tumors that meet all inclusion and exclusion criteria may be ablated during a single session as part of this protocol. The second tumor may only be ablated if its planned ablation zone does not overlap with the ablation zone of the previously ablated tumor.

If a subject had three oligometastatic tumors that met all inclusion and exclusion criteria, but only two could be treated, per protocol, on the "Ablation Visit", the third, non-target tumor may be ablated at a later study visit. Similarly, if a new, non-target oligometastatic tumor is identified during study follow-up that meets all inclusion and exclusion criteria, it may be ablated. However, only up to three total oligometastatic lung tumors ("target" or "non-target") may be ablated as part of this protocol during the 12-month follow-up period.

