If target tumors recur after the original ablation, they may be re-ablated after the Visit 3 assessment for Technique Efficacy has been completed. A re-ablation will not change or extend the follow-up schedule. Additionally, no single tumor should be ablated more than twice during the 12-month follow-up period (i.e., the original ablation procedure and a re-ablation procedure at a separate visit). **Robotic Navigation Portion of Procedure**

Cone beam CT will be used in all cases to confirm the presence of the tumor(s) immediately before initiating the procedure. Navigation to the target tumor(s) will be performed using the MONARCH Platform. The MONARCH Platform is a novel robotic-assisted, software driven, endoscope articulation system which can electromechanically insert, steer, and withdraw a flexible endoscope to patient airways under continuous, real-time, direct, visual control by a physician operator.

Users must follow all instructions for use supplied with the MONARCH Platform, its components, instruments, and accessories, including any instructions for use (IFUs) provided with instruments or accessories. The provided IFU is the primary source for detailed safety information. The MONARCH Platform and its accessories are intended to provide bronchoscopic visualization of and access to patient airways for diagnostic and therapeutic procedures.

Microwave Ablation Portion of Procedure

The ablation will be performed using the NEUWAVE FLEX MC Microwave Ablation System, per the device's User Manual and Instructions for Use (IFU), and the performing physician's clinical judgment.

All ablations will be performed under general anesthesia via a transbronchial approach. Prophylactic antibiotics should be administered pre-ablation per site SOC.

The size of the tumor(s) will be measured and recorded on the day of ablation (Visit 2). Afterwards, the Monarch Platform will be used to navigate the microwave ablation probe to the target tumor and CBCT will be used to confirm probe position/placement.

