12.3 Data Safety Monitoring Board

An independent DSMB will be commissioned to review, on a regular basis, safety data from the study. The DSMB will advise the Sponsor regarding the continuing safety of subjects and those yet to be recruited to the study. The initial DSMB review of safety data will be conducted after five subjects have been ablated and completed the 30-day follow-up visit. Additional DSMB reviews will occur after 10 and 20 subjects have been ablated and completed the 30-day follow-up visit. After the review of the initial 20 subjects, the DSMB will determine the appropriate continued frequency for their reviews, which will continue for the duration of the study. Based on accumulating safety data from the study, the DSMB may recommend whether to continue, suspend, modify, or stop the study.

At the conclusion of the review of all enrolled and ablated subjects, the DSMB will also give a final assessment of the safety of the procedure. The composition, responsibilities, frequency of DSMB meetings, handling of emergency situations, and documentation of DSMB meetings is specified in the DSMB Charter.

Additionally, the DSMB will review all reported deaths. A report of death or severe hemorrhage requiring intervention beyond local therapy (i.e., Nashville \geq grade 2 or CTCAE \geq grade 2) within 30 days of the procedure will put enrollment on hold and require review by the DSMB to

determine if the death or hemorrhage was related to the ablation procedure. The DSMB will determine whether the study may resume enrollment or state other necessary conditions or recommendations to resume enrollment.

A document outlining membership and responsibilities will be described in detail in a separate charter, which will be finalized prior to the first subject being ablated.

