## **9 Data Safety Monitoring Board (DSMB)**

An independent data and safety monitoring board (DSMB) will be commissioned to review, on a regular basis, safety data from the study. The DSMB will advise the Sponsor regarding the continuing safety of subjects and those yet to be recruited to the study. The initial DSMB review of safety data will be conducted after five subjects have been ablated and completed the 30-day follow-up visit. Additional DSMB reviews will occur after 10 and 20 subjects have been ablated and completed the 30-day follow-up visit. After the review of the initial 20 subjects, the DSMB will determine the appropriate continued frequency for their reviews, which will continue for the duration of the study. Based on accumulating safety data from the study, the DSMB may recommend whether to continue, suspend, modify, or stop the study.

At the conclusion of the review of all enrolled and ablated subjects, the DSMB will also give a final assessment of the safety of the procedure. The composition, responsibilities, frequency of DSMB meetings, handling of emergency situations, and documentation of DSMB meetings is specified in the DSMB Charter.

Additionally, the DSMB will review all reported deaths. A report of death or severe hemorrhage requiring intervention beyond local therapy (i.e., Nashville  $\geq$  grade 2 or CTCAE  $\geq$  grade 2) within 30 days of the procedure will put enrollment on hold and require review by the DSMB to determine if the death or hemorrhage was related to the ablation procedure. The DSMB will determine whether the study may resume enrollment or state other necessary conditions or recommendations to resume enrollment.

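### The automatic safety hold stops only enrollment, so it does not pause later ablations in subjects already treated

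*Protocol*

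**What the plan says.** The hold is triggered by a death, or by bleeding of Nashville or CTCAE grade 2 or worse, within 30 days of an ablation. It is stated four times:

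- Protocol Summary, DSMB row: such a report "within 30 days of an ablation procedure will temporarily stop enrollment and require review by the DSMB".
- Protocol 12.2: it "will put enrollment on hold and require an investigation to determine if the death or hemorrhage was related to the ablation procedure"; the DSMB leads that investigation.
- Protocol 12.3: it "will put enrollment on hold and require review by the DSMB".
- SAP 9 repeats 12.3.

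The release appears in protocol 12.3 and SAP 9: "The DSMB will determine whether the study may resume enrollment or state other necessary conditions or recommendations to resume enrollment".

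Protocol 6.1 provides for FLEX MC procedures after the index ablation:

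- Re-ablation: "If target tumors recur after the original ablation, they may be re-ablated after the Visit 3 assessment for Technique Efficacy has been completed".
- A third tumor left untreated at the index visit: "the third, non-target tumor may be ablated at a later study visit".
- A tumor found later: "if a new, non-target oligometastatic tumor is identified during study follow-up that meets all inclusion and exclusion criteria, it may be ablated".

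**The concern.** The hold exists so that the DSMB can establish whether a death or serious bleed was caused by the ablation procedure. While that question is open, the same procedure in a treated subject pauses only if someone chooses to pause it.

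The automatic part of the rule protects future subjects. Subjects already in the study who are due another ablation depend on discretion. Protocol 12.3 itself gives the DSMB a remit covering both current subjects and those not yet recruited, but the automatic action is defined for recruitment only.

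**Working it through.** The point concerns the scope of wording, and the plan gives no figure to reproduce. The check sets the hold against the uses of the word *enrollment* and against the later procedures.

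**Step 1. What each hold statement stops and releases.**

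| Place | Action named | Release named |
|---|---|---|
| Protocol Summary | Stop to enrollment, DSMB review | None |
| Protocol 12.2 | Hold on enrollment, DSMB-led investigation | None |
| Protocol 12.3 | Hold on enrollment, DSMB review | Resuming enrollment |
| SAP 9 | As 12.3 | As 12.3 |

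None mentions ablations, re-ablations or procedures as things that pause.

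**Step 2. Is a treated subject past enrollment on every usage?** The protocol uses the term in three ways.

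| Usage | Source | Treated subject | Consented, not yet ablated |
|---|---|---|---|
| Enrolled at consent signature | 5.2 | Past it | Past it |
| Enrolled after consent and meeting entry criteria | 5.1 | Past it | Past it once criteria are met |
| Enrollment as a process running until subjects are treated or ablation is initiated | 5.1, 5.2 | Past it | Still within it |

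For treated subjects all three agree: a hold on enrollment does not reach them. For consented subjects not yet ablated the usages disagree.

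**Step 3. Can treated subjects have the procedure again?** Yes. Protocol 6.1 allows re-ablation of a recurrent target tumor once the Visit 3 assessment is complete. Section 4.0 places non-target ablations after the same assessment. No text in the protocol or SAP suspends either during a hold.

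**Step 4. Trigger and action do not match.** The Summary trigger is an event after an ablation procedure, not only the index one, so an event after a re-ablation can start a hold that does not name other re-ablations. Elsewhere the protocol does name them: adverse event capture in 12.0 runs "through 30-days post any ablation procedure (i.e., the original ablation as well as any re-ablation".

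**Step 5. How long can the hold be without effect?** The Summary plans 2 years of enrollment and 1 year of follow-up, and 5.1 follows each subject for 12 months from the first ablation.

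- Planned duration: 24 + 12 = 36 months.
- Period after the last index ablation: 12 months, or 12/36 = one third.

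In that period a triggering event still requires DSMB review, but no enrollment is left to stop. This assumes that the planned timelines hold and that the last index ablation falls at the end of the enrollment period.

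**The case against.** The strongest reply is that the plan has other brakes and that a discretionary approach is defensible:

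- The DSMB may recommend suspending, modifying or stopping the study, and its release decision may attach further conditions (12.3, SAP 9).
- Its remit expressly includes the continuing safety of current subjects.
- Section 2.0 allows departure from the plan without prior IRB/EC approval to remove an immediate hazard, so a pause need not wait for an amendment.
- Further stopping rules may be added (12.2), and the sponsor may terminate a site or the study (5.7).
- A new non-target tumor must meet all entry criteria, so exclusion 24 lets the investigator decline.
- Discretion worked in the one precedent described. After a periprocedural death in the pilot, the sponsor stopped the study although the DSMB would have let it continue with modifications (3.0).
- An automatic halt has a price. Nashville grade 2 can be reached by suctioning for over a minute or by using cold saline (Appendix 2), and a halt may delay treatment of recurrent cancer.
- The DSMB Charter, which covers emergencies, the Safety Management Plan and the Safety Monitoring Plan were not available and may settle the matter.

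Much of this stands. It shows that a pause is possible and that the practical gap may be small. It does not make the pause automatic, because each visible safeguard requires someone to decide. The sponsor's stated power to pause (5.1) concerns enrolling new subjects, and 6.1 states no repeat eligibility check for re-ablation. If the companion documents already cover these procedures, the protocol and SAP still need to agree with them.

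**Conclusion.** The point holds for subjects already treated. As worded, the automatic hold does not pause re-ablations or non-target ablations, and after accrual and index treatment are complete it stops nothing. It is a cheap improvement to patient safety. Confidence is medium, because three companion documents were not seen.

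Three stronger readings are not supported:

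- *That the plan directs procedures to continue during a hold, or leaves treated subjects unprotected.* Later ablations are permitted, not required, and the discretionary safeguards are real.
- *That subjects consented or rescheduled but not yet ablated fall outside the hold.* The consent-based definition in 5.2 suggests this, but 5.1 and 5.2 also describe enrollment as running until ablation or treatment. On that usage a hold plausibly covers first ablations. The text is ambiguous, no more.
- *That the number of re-ablations exposed during a hold can be calculated by applying a recurrence rate to 145 subjects.* The single pilot recurrence (3.0) is not stated to be local. Re-ablations cannot be spread evenly over the study, because they are barred until after Visit 3. No hold duration is given, and non-target ablations cannot be counted at all.

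The case therefore rests on the seriousness of the triggering events and the low cost of the change, not on frequency.

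**What to change.** 1. In the protocol Summary, protocol 12.2, protocol 12.3 and SAP 9, state that a triggering event pauses new enrollment and all study FLEX MC procedures (index, rescheduled, re-ablation and non-target) until the DSMB releases them, and that the DSMB may release individual subjects case by case. This also removes the ambiguity about subjects not yet ablated.
2. Word the release in protocol 12.3 and SAP 9 to match: *resume enrollment and procedures*.
3. If the 30-day screening window (7.1) lapses during a hold, repeat the screening assessments, including the chest CT. Do not simply pause the window: eligibility on tumor size rests on the screening image and is not re-confirmed on the day of ablation (5.3, Note 1), so a paused window would allow ablation on out-of-date imaging. Say that this overrides the allowance in 5.4 Note 3 to repeat only INR on rescheduling.
4. Align the DSMB Charter, and check the two safety plans for consistency.

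The cost is a sentence or two in four places, a short rule on screening, and an amendment needing IRB/EC approval at about 15 sites. Some treatments, including re-ablation of recurrent tumor, would be briefly delayed, and some screening, with its CT exposure, would be repeated. Holds may recur because Nashville grade 2 is a low trigger. Case-by-case release limits the delay, at the price of returning part of the decision to the DSMB's judgment.
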